## Adverse Events

An adverse event is any untoward medical occurrence in a participant, whether or not is is causally related to the study. An adverse event can therefore be any unfavorable and unintended sign (including an abnormal laboratory finding, for example), symptom or disease temporally associated with the study.

Adverse events will be recorded on the appropriate case report forms and source documents. The investigator and/or trained staff member will evaluate all adverse events as to their severity and relation to the test article. The severity of adverse events will be graded as follows:

Mild: Awareness of a sign or symptom but easily tolerated.

Moderate: Discomfort sufficient to cause interference with usual activity or to affect clinical status.

Severe: Incapacitating with inability to do usual activity or to significantly affect clinical status.

Life Threatening: The participant was at immediate risk of death from the adverse event as it occurred.

The Investigator will also assess the relationship of any adverse event to study, based upon available information, using the following guidelines:

0 = Unlikely: No temporal association, or the cause of the event has been identified. 1 = Possible: Temporal association, but other etiologies are likely to be the cause; however, involvement of the study procedures cannot be excluded.

2 = Probable: Temporal association, other etiologies are possible, but not likely.

A *serious adverse event* is any experience that results in any of the following outcomes: death, is life threatening, results in inpatient hospitalization or prolongation of hospitalization, a persistent or significant disability/incapacity.

Important medical events that may not result in death, be life-threatening, or require hospitalization may be considered a serious adverse event when, based upon appropriate medical judgment, they may jeopardize the patient or participant and may require medical or surgical intervention to prevent one of the outcomes listed in this definition.

Side effects associated with tDCS according to the most recent data available (Brunoni, Fregni, & Pagano, 2011; Nitsche et al., 2008; Antal et al, 2007; Moliadze, Antal, & Paulus, 2010; Brignani, Ruzzoli, Mauri, & Miniussi, 2013) are:

Sensations reported by subjects under the electrodes: (These sensations can sometimes continue throughout and for a brief period following completion of the tDCS but usually resolve shortly after the initiation of tDCS)

Mild tingling (20-70%)

Light itching (30-40%)

Slight burning (10-22%) Discomfort or mild pain (10-18%)

Other effects that can occur both during and after tDCS include: Skin redness (20%)

Mild fatigue (15%)

Headache (10-15%)

Difficulties in concentration (11%)

Additionally the following rare side effects have been described: Nausea (<1%)

Nervousness (<1%)

Although it has never been reported in tDCS, seizures are a theoretical risk. Individuals with a history of seizures and/or a diagnosis of epilepsy will therefore be excluded from this study. EEG has not associated adverse events and is considered safe and painless.

All adverse events, Serious Adverse Events and Unanticipated Problems will be reported to the Advarra IRB according to its policies.

### Risks

The medical risks are described in the adverse event section. Other risks related to the loss of confidentiality are described in the confidentiality section with steps we will take to mitigate any such risk.

*Participant Burden:* Participation in this protocol will require moderate subject time and effort. Therefore, in addition to recommended safety measures described below, additional efforts will be taken to minimize subject burden and maximize retention throughout the study. It is of note that our study team has a strong track record of successful clinical research requiring similar participation and retention has been high in these efforts.

Several strategies will be employed to minimize subject burden and maximize adherence to the protocol.

Specifically we will:

- Develop a personal relationship between subjects and members of the staff by matching research assistants with individual participants.
- Schedule appointments at convenient times with familiar staff.
- Explain to subjects all aspects of their participation.

- Provide reminders of all appointments.
- Include personal notes in the subject's data file to remember events in the life of the participant; these can be commented on at future visits (e.g. birth of a grandchild)

Any participant who suffers an adverse event during the conduct of study protocols will be triaged immediately by the medical investigators, and the study psychiatrist. The study PI and study psychiatrist will monitor and manage all study related A/E's. If follow up care is needed to treat an A/E, the investigators will arrange to have this care provided at a nearby institution, convenient to the study participant. . The treating provider will bill the insurance company or other third parties, if appropriate, for the care a participant receives for any injury. We will try to have these costs paid for, but the participant may be responsible for some of them. For example, they may be responsible for payment of any deductibles and co-payments required by the insurer. There are no plans to provide any compensation for an injury beyond what is described above, should one occur.

If there is a change in the clinical condition of the participant, the study psychiatrist will contact the subject's treating/primary psychiatrist so that appropriate primary clinical care can be provided.

If, during the course of this study, the participant experiences an urgent medical need, he/she will be advised to seek immediate medical care, including contacting their primary care physician/psychiatrist as indicated.

There is no cost to the participant or insurer for the device.

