### Visits (All visits will be conducted remotely)

For this study, participant caregiver administrators will be provided remote step-by-step training to administer the tDCS sessions to the participants with MDD. Participant caregiver-administrators will be directly supervised remotely, until they demonstrate proficiency, without coaching by the study team. We have developed a step by step training manual, and have successfully trained older adult caregivers to administer the tDCS.

Visit	Purpose	Procedures	Study personnel	Duration	Location
Pre-ICF	Advance review	Informed consent pre-review by potential participants	RA will send	As needed for review	Mailed/emailed to P
Visit 1	Remote screen and assessment visit	Informed consent [ P with MDD ] Mental Health/Medical health history; medications; Cognitive Assessment; Interview with study psychiatrist [ Participant caregiver-administrators ] Health history; computer proficiency questionnaire [ Both participants ] tDCS overview and training	Study research assistant; Study psychiatrist	~ 1 hour	Remote
Home tDCS administration Treatment period – Daily tDCS sessions over 4 weeks *Participant ratings of suicidality will be completed each day, and responses will be monitored and immediately be reviewed in real time by the study RA and study psychiatrist. Any changes from baseline will result in an immediate contact to the participant by the study psychiatrist.					
Week (Wk)1; Day (D) 1	Home-based tDCS	At-home tDCS equipment set-up; tDCS administration by caregiver-administrator with step-by- step remote training by study staff Daily diary	Study research assistant	1 hour total (tDCS session=30 mins)	Video conference
Wk1, tDCS session	Home-based tDCS once a day	tDCS admin by the caregiver-administrator with remote staff oversight and coaching Daily	Study research assistant	1 hour total (tDCS session=30)	Video conference

D 2-4		diary		mins)	
Wk 1, tDCS session D 5	Home-based tDCS	tDCS admin by the caregiver-administrator with remote staff oversight and coaching; Staff administered skills test for caregiver-administrators Daily diary	Study research assistant	1 hour total (tDCS session=30 mins)	Video conference
Wk 1-4; D6-28	Home-based tDCS once a day	The caregiver-administrator will administer the in-home tDCS session with remote staff monitoring and video conferencing if necessary Daily diary	Study research assistant	1 hour	Participant's Home

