Wks 1-4, D 7, 14, 21, and 28	Weekly assessments	Participants with MDD only Week 1-4 Assessment completion (Day 7, 14,21, and 28); depression symptoms and quality of life assessments	Study research assistant	30 minutes	Phone
Home tDCS administration Treatment taper period – weeks 5-8 Participant ratings of suicidality will be completed each day, and responses will be monitored and immediately be reviewed in real time by the study RA and study psychiatrist. Any changes from baseline will result in an immediate contact to the participant by the study psychiatrist.					
Wk 5, D 30,32,34	Home-based tDCS Total of 3 sessions, one every other day over a 6 day period.	The caregiver-administrator will administer the in-home tDCS session with remote staff monitoring and video conferencing if necessary Daily diary	Study research assistant	1 hour	Participant's Home
Wk 6-7, D 37,40, 43	Home-based tDCS Total of 3 sessions, one every third day over a 9 day period	The caregiver-administrator will administer the in-home tDCS session with remote staff monitoring and video conferencing if necessary Daily diary	Study research assistant	1 hour	Participant's Home
Wk 8 D 47,51, 55	Home-based tDCS Total of 3 sessions, one every fourth day over a 12 day	The caregiver-administrator will administer the in-home tDCS session with remote staff monitoring and video conferencing if necessary Daily diary	Study research assistant	1 hour	Participant's Home

	period				
Wks 5-8 D35, 42, 49, 56	Weekly assessments	Participants with MDD only Weeks 5-8 Assessment completion (Day 35, 42,49, and 56); depression symptoms and quality of life assessments	Study research assistant	30 minutes	Phone
Home tDCS administration completed after Week 8, Day 55 session. Return of Home tDCS equipment to research team in the provided shipping materials and label.					
Four week follow-up period – weeks 9-12					
Wks 9- 12 D57-84	Four week follow-up period	Participants with MDD only The study research assistant will maintain weekly contact with the participant over the 4 week follow-up period	Study research assistant	20 minutes	Phone
Week 12, Day 84	Final study assessment	Both participants: Final assessment completion, depression symptoms, quality of life assessments, cognitive assessment	Study research assistant	1 hour	Phone
End of study: Results sent to participant with MDD and treating psychiatrist					

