## Statistical Methods and Analysis

### *Primary*

Feasibility and tolerability/safety will be evaluated using home-based data as it is collected by reported number of aborted sessions.

The *primary outcome* will be change in the observer rated MADRS score from baseline to the 1-month follow-up.

Clinical response is defined as  $\geq 50\%$  improvement in MADRS score from baseline to the 1-month follow-up. Remission is defined as a MADRS score  $\leq 10$ .

The *secondary outcome* measures will include the participant-rated Quick Inventory of Depressive Symptomatology (QIDS-SR) (Rush et al., 2003) and the Quality of Life Enjoyment and Satisfaction Questionnaire Short Form (Q-LES-Q-SF) (Endicott et al., 1993), both administered at the same time points as the MADRS. A computer-based cognitive test battery, CogState (<https://www.cogstate.com>), will provide an additional safety outcome measure. This battery includes tests designed to assess verbal learning and memory (International Shopping List Task), attention and psychomotor function (Detection Task), visual attention (Identification Task), visual learning and memory (One Card Learning Task), working memory (Two Back Task), and executive function (Set Shifting Task).

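### Nothing in the plan keeps the research assistant matched to a participant from scoring the observer-rated MADRS, or keeps rater role and contact mode the same at baseline and follow-up; a low-cost change would fix both

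*Combined protocol and SAP*

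**What the plan says.** **Staffing.** Under Risks (Participant Burden), the plan intends to "Develop a personal relationship between subjects and members of the staff by matching research assistants with individual participants" and to "Schedule appointments at convenient times with familiar staff".

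**Sessions.** In the Visits table the study research assistant is the only personnel listed for all session rows. Day 1 is step-by-step remote training. Days 2–5 are "tDCS admin by the caregiver-administrator with remote staff oversight and coaching". From Day 6, and through the taper, the role is remote monitoring, with video only when needed.

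**Assessments after baseline.** The same role is the only one listed, by phone, for the weekly rows (for example "Week 1-4 Assessment completion (Day 7, 14,21, and 28); depression symptoms and quality of life assessments"), for their counterparts on Days 35–56, and for Day 84: "Final assessment completion, depression symptoms, quality of life assessments, cognitive assessment".

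**Baseline.** Visit 1 is remote and lists both a research assistant and the study psychiatrist. Its procedures include "Interview with study psychiatrist". The inclusion criteria require a MADRS of at least 20, so a baseline score must exist, but its rater is not named.

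**Outcome.** Statistical Methods and Analysis defines the primary outcome as "change in the observer rated MADRS score from baseline to the 1-month follow-up". The two participant-rated scales are given when the MADRS is given. The Primary Analysis Plan for efficacy analyses the median percentage change, calls the study a pilot for estimating effect sizes, and says significance is not an aim.

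**The concern.** The MADRS is the only observer-rated scale among the outcomes, so its value depends partly on who rates it. The staffing text favours continuity between one assistant and one participant. The Visits table then gives session support and follow-up assessment to that same role. Nothing separates the two tasks, and nothing holds the rater role or contact mode constant from baseline to follow-up.

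Two components of error follow. An assistant who trained and encouraged a participant may score follow-up more favourably, or the participant may report more favourably to a familiar coach. Separately, if the psychiatrist rates baseline and an assistant rates follow-up by phone, any systematic difference between the two becomes part of the change score.

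There is no control arm in which such a difference would also appear and be subtracted. It would pass into the effect size that the pilot exists to provide, and it cannot be removed once the ratings are made.

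**Working it through.** **1. Who can rate the MADRS.** No figure in the plan can be reproduced here, so this step sets the text side by side.

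| Time | Task | Personnel listed | Contact |
|---|---|---|---|
| Visit 1 | History, psychiatrist interview, training overview | Research assistant; study psychiatrist | Remote |
| Days 1–5 | Training and coaching | Research assistant | Video |
| Days 6–28 and 9 taper sessions | Monitoring | Research assistant | Remote, video when needed |
| Days 7–28 and 35–56, weekly | Depression and quality-of-life assessments | Research assistant | Phone |
| Day 84 | Final assessment | Research assistant | Phone |

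The table refers to depression symptoms and does not name the MADRS. The link is an inference, but a strong one, because no other row after baseline could hold a MADRS rating. The 1-month follow-up could mean Day 28 or Day 84; the same role is listed at both. The table names a role. That coach and rater would tend to be the same person follows from the matching and familiar-staff bullets.

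**2. What enters the effect size.** Write each score as the true value plus rater error: baseline B + e0, follow-up F + e1. The observed change is (F − B) + (e1 − e0). Leniency that is equal at both ratings cancels in the absolute change. Only the net shift d = e0 − e1 matters, with d > 0 meaning a more lenient follow-up rating.

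**3. Illustration of scale.** Means of 27.5 at baseline and 15.5 at follow-up come from the open-label home-tDCS trial described in the plan's tDCS background. The following are assumptions: SD 4–6 at baseline, SD 7–11 at follow-up, correlation 0.2–0.5, and d of 1, 2 or 3 points.

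*Analysed measure, median percentage change.* An approximation at the means is 100 × (15.5 − d − 27.5)/27.5:
- d = 0: −12/27.5 = −43.6%
- d = 1: −13/27.5 = −47.3%
- d = 2: −14/27.5 = −50.9%
- d = 3: −15/27.5 = −54.5%

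Simulating bivariate normal scores with baseline restricted to at least 20 gives a median of about −42% to −45% with no shift. It moves by about 3.5, 7 and 10.5 percentage points for d = 1, 2 and 3.

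*Response (at least 50% improvement).* A participant responds if F − d ≤ 0.5B. The quantity F − 0.5B has mean 15.5 − 13.75 = 1.75 and variance s1² + 0.25·s0² − ρ·s0·s1, where s0 and s1 are the baseline and follow-up SDs and ρ the correlation. Without the baseline restriction:
- s0 = 4, s1 = 7, ρ = 0.5: variance 49 + 4 − 14 = 39, SD 6.24. Response is Φ(−1.75/6.24) = 39.0% with no shift and Φ(0.25/6.24) = 51.6% with d = 2, a rise of 12.6 points.
- s0 = 4, s1 = 11, ρ = 0.2: variance 121 + 4 − 8.8 = 116.2, SD 10.78. Response is 43.6% with no shift and 50.9% with d = 2, a rise of about 7.4 points.

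The simulation with the baseline restriction, over the full ranges:

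| Net shift d | Median % change moves by | Response rate rises by |
|---|---|---|
| 1 | about 3.5 points | 4–6 points |
| 2 | about 7 points | 7–13 points |
| 3 | about 10.5 points | 11–20 points |

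**The case against.** **What stands.** The Visits table names a role, not a person, and never names the MADRS. A reader might infer that the plan designates the matched coach as MADRS assessor. It does not; it leaves the rater unspecified and allows the coach to be one. The MADRS form and training manual are listed but not reproduced, so rater instructions in them cannot be excluded.

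Coaching is confined to Days 1–5. A reader might count all 28 + 9 = 37 sessions as coached, but from Day 6 the listed role is monitoring. Coaching ends 79 days before Day 84, although weekly phone contact continues.

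The size of the shift is assumed. A reader might set the response-rate movement against the 30.9% versus 18.9% active-sham difference (12.0 points) in the cited individual-patient-data meta-analysis. That is a between-arm contrast, and this study makes no such comparison.

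An unmatched rater is not a blinded rater. Everyone knows the treatment is active, and placebo response and regression to the mean stay in the estimate whoever rates. The participant-rated QIDS-SR, already collected alongside, gives some cross-check.

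The stated primary objective is feasibility, adherence and safety, with clinical improvement as secondary pilot data.

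**What does not stand.** The low priority of significance testing does not remove the issue, because the same sentence makes effect sizes the purpose. Nor is this only missing detail: followed as written, the staffing text steers rating towards the matched assistant.

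**Conclusion.** The point holds as a low-cost improvement. The plan permits, and its staffing text favours, rating of the observer-rated MADRS by the assistant who trained and coached the participant. It also leaves rater role and contact mode free to change between baseline and follow-up. In an uncontrolled study, any net rating difference is carried in full into the effect size.

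The illustrated movement of about 3.5, 7 or 10.5 percentage points in the median percentage change rests on the assumed means, SDs, correlations and a chosen shift of 1–3 points. The documents do not show that such a shift would occur, and they do not support a claim that the MADRS result will be biased by any particular amount. They support only the statement that nothing in the plan guards against these two components.

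**What to change.** In the Visits table and in Statistical Methods and Analysis, state that:
- baseline and follow-up MADRS are scored by the same rater role and through the same contact mode;
- the rater is an existing research assistant not matched to that participant or, if only one assistant is available, the study psychiatrist;
- the rater does not see earlier MADRS scores or the session log.

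Matching for training and retention stays, as does the daily suicidality review as currently assigned. Sample size, visits and instruments do not change.

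**Cost.** Protocol wording and cross-scheduling of rating calls, which would come from a less familiar person and so cut slightly against the familiar-staff strategy. The number of assistants is not documented. The Risks section uses the plural, but other text refers to a single study assistant, so it cannot be assumed that assistants can rate each other's participants; the psychiatrist is the fallback for that reason.

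**Limit.** The change removes the coach-familiarity and rater-change components only. General open-label expectancy remains, and the report should say so.

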## Benefits

While there are no definitive benefits to participants as a result of participation in this study, MDD participants who received tDCS interventions in prior studies showed improvement of symptoms.

Most recently, Razza et al. (2020) completed a systematic review of all studies of tDCS for treatment of acute major depressive episodes completed up to January 2020. They included all randomized, sham-controlled clinical trials (RCTs) enrolling participants with an acute depressive episode, a total of 23 RCTs with 1,092 participants. They found that active tDCS was superior to sham regarding endpoint depression scores, response and remission rates. Moreover, active tDCS was safe with a side-effect profile comparable to sham.

Moffa et al. (2020) also recently published an individual patient data (IPD) meta-analysis evaluating the efficacy and acceptability of tDCS for treatment of acute major depressive episodes. The IPD meta-analysis is more accurate in estimating the efficacy of an intervention and also superior to the aggregated data approach for obtaining predictors of treatment outcome since it uses the raw data of each participant collected from each study (Riley et al., 2010). Moffa et al. included data from all published placebo-controlled trials on tDCS as only intervention in MDD conducted until December-2018. This included 9 eligible studies with a total of 572 participants. They found active tDCS to be significantly superior to sham for an antidepressant response (30.9% vs. 18.9% respectively; OR = 1.96), remission (19.9% vs. 11.7%, OR = 1.94), and depression improvement (effect size  $\beta = 0.31$ ). Moreover, they found a consistent continuous clinical improvement after the end of the tDCS treatment course. It is noteworthy that the clinical efficacy was substantially higher in the studies where the tDCS course was longer (3-4 weeks versus 1-2 weeks).

The ultimate goal of this work is to identify the potential of tDCS as a home therapy to induce improvements of MDD for patients with the disease. We anticipate that this specific study will demonstrate that remote tDCS sessions are feasible in this population, and offer an important and convenient alternative for multi-session tDCS administration in adults with MDD.

### Visits (All visits will be conducted remotely)

For this study, participant caregiver administrators will be provided remote step-by-step training to administer the tDCS sessions to the participants with MDD. Participant caregiver-administrators will be directly supervised remotely, until they demonstrate proficiency, without coaching by the study team. We have developed a step by step training manual, and have successfully trained older adult caregivers to administer the tDCS.

Visit	Purpose	Procedures	Study personnel	Duration	Location
Pre-ICF	Advance review	Informed consent pre-review by potential participants	RA will send	As needed for review	Mailed/emailed to P
Visit 1	Remote screen and assessment visit	Informed consent [ P with MDD ] Mental Health/Medical health history; medications; Cognitive Assessment; Interview with study psychiatrist [ Participant caregiver-administrators ] Health history; computer proficiency questionnaire [ Both participants ] tDCS overview and training	Study research assistant; Study psychiatrist	~ 1 hour	Remote
Home tDCS administration Treatment period – Daily tDCS sessions over 4 weeks *Participant ratings of suicidality will be completed each day, and responses will be monitored and immediately be reviewed in real time by the study RA and study psychiatrist. Any changes from baseline will result in an immediate contact to the participant by the study psychiatrist.					
Week (Wk)1; Day (D) 1	Home-based tDCS	At-home tDCS equipment set-up; tDCS administration by caregiver-administrator with step-by- step remote training by study staff Daily diary	Study research assistant	1 hour total (tDCS session=30 mins)	Video conference
Wk1, tDCS session	Home-based tDCS once a day	tDCS admin by the caregiver-administrator with remote staff oversight and coaching Daily	Study research assistant	1 hour total (tDCS session=30)	Video conference

D 2-4		diary		mins)	
Wk 1, tDCS session D 5	Home-based tDCS	tDCS admin by the caregiver-administrator with remote staff oversight and coaching; Staff administered skills test for caregiver-administrators Daily diary	Study research assistant	1 hour total (tDCS session=30 mins)	Video conference
Wk 1-4; D6-28	Home-based tDCS once a day	The caregiver-administrator will administer the in-home tDCS session with remote staff monitoring and video conferencing if necessary Daily diary	Study research assistant	1 hour	Participant's Home
Wks 1-4, D 7, 14, 21, and 28	Weekly assessments	Participants with MDD only Week 1-4 Assessment completion (Day 7, 14,21, and 28); depression symptoms and quality of life assessments	Study research assistant	30 minutes	Phone
Home tDCS administration Treatment taper period – weeks 5-8 Participant ratings of suicidality will be completed each day, and responses will be monitored and immediately be reviewed in real time by the study RA and study psychiatrist. Any changes from baseline will result in an immediate contact to the participant by the study psychiatrist.					
Wk 5, D 30,32,34	Home-based tDCS Total of 3 sessions, one every other day over a 6 day period.	The caregiver-administrator will administer the in-home tDCS session with remote staff monitoring and video conferencing if necessary Daily diary	Study research assistant	1 hour	Participant's Home
Wk 6-7, D 37,40, 43	Home-based tDCS Total of 3 sessions, one every third day over a 9 day period	The caregiver-administrator will administer the in-home tDCS session with remote staff monitoring and video conferencing if necessary Daily diary	Study research assistant	1 hour	Participant's Home
Wk 8 D 47,51, 55	Home-based tDCS Total of 3 sessions, one every fourth day over a 12 day	The caregiver-administrator will administer the in-home tDCS session with remote staff monitoring and video conferencing if necessary Daily diary	Study research assistant	1 hour	Participant's Home

	period				
Wks 5-8 D35, 42, 49, 56	Weekly assessments	Participants with MDD only Weeks 5-8 Assessment completion (Day 35, 42,49, and 56); depression symptoms and quality of life assessments	Study research assistant	30 minutes	Phone
Home tDCS administration completed after Week 8, Day 55 session. Return of Home tDCS equipment to research team in the provided shipping materials and label.					
Four week follow-up period – weeks 9-12					
Wks 9- 12 D57-84	Four week follow-up period	Participants with MDD only The study research assistant will maintain weekly contact with the participant over the 4 week follow-up period	Study research assistant	20 minutes	Phone
Week 12, Day 84	Final study assessment	Both participants: Final assessment completion, depression symptoms, quality of life assessments, cognitive assessment	Study research assistant	1 hour	Phone
End of study: Results sent to participant with MDD and treating psychiatrist					

Daily sessions (28 daily sessions): The device will be used to apply 20 minutes of tDCS to the participant with MDD's scalp in each of 28 daily sessions.

Thereafter, participants with MDD will undergo a taper phase of an additional 9 sessions of tDCS applied in progressively decreasing frequency until day #60 of the study as follows:

- (1) First taper phase: three 30 minutes tDCS sessions applied every other day;
- (2) Second taper phase: three 30 minutes tDCS sessions applied one every third day;
- (3) Third and final taper phase: three final 30 minutes tDCS sessions applied one every fourth day.

The study team will predetermine, with the participant team, their most convenient two hour window for the home administration. During remote tDCS administration, the study team will be notified electronically by email when the tDCS session has been started and also when it has been completed, or if the tDCS session was aborted, or not completed during the predetermined two hour window.

The device will contain a sequence of simplified screen prompts for the participant,. To move to the next screen the participant will press a circle on the screen to continue (or to stop)

For example:

1. Hello
2. Battery status is GOOD
3. Today is Monday (date) It is now ( ) o'clock
4. Wear the Cap

5. Check the electrodes - 1 green is in the 1 green hole and secure, 2 yellow is in the 2 yellow hole and secure.
6. Are you ready for your 30 minutes session? If yes, press continue
7. Session has started, please stay in place until session is over [clock appears on screen to count down the minutes]
8. Session has ended, please stay in place while the device powers off.
9. Session is now completed! You may turn off the tablet, and remove the cap and electrodes

Daily sessions (28 daily sessions): The device will contain a block that will only allow one session to be administered within a 24 hour period. If a session is started and aborted, the participant will not be able to administer a new session until the next day, 24 hours later.

During the taper phase - the device block will only allow:

First taper phase: Three sessions, one every other day. If a session is started and aborted, the participant will not be able to administer a new session until 48 hours later. After the 3 sessions have been administered, (which will include any session that was started and aborted), a new session will not be available until the next scheduled session. The study team will monitor participant study adherence through completed sessions and through video conferencing and telephone contact.

Second taper phase: Three sessions, once every third day. If a session is started and aborted, the participant will not be able to administer a new session until 72 hours later. After the 3 sessions have been administered, (which will include any session that was started and aborted), a new session will not be available until the next scheduled session. The study team will continue to monitor participant study adherence through completed sessions and through video conferencing and telephone contact.

Third and final taper phase: Three sessions, once every fourth day. If a session is started and aborted, the participant will not be able to administer a new session until 96 hours later. After the 3 sessions have been administered, (which will include any session that was started and aborted), the sessions will be completed.

